6 ANALYSIS

The first subsections of this section 6, describes general strategies applying to all analyses unless otherwise specifically stated. Subsection 6.8 contains the separate analysis strategies per outcome in 6.8.x.

6.1 COVARIATE ADJUSTMENT IN GENERAL

Analyses will be adjusted for the three stratification variables, and no other, complying with RCT analysis guidelines from European Medicines Agency⁵.

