1.2 SAP VERSION

This is the second version of the SAP.

¹ <https://clinicaltrials.gov/ct2/show/NCT02872051>

² <https://clinicaltrials.gov/ct2/show/NCT02885519>

Differences between version 1 and 2 are explicitly stated through a .docx-version of this newest version, where all changes are tracked, using the *Track changes* function in Microsoft Office Word. This file will be readily mailed through the corresponding author.

In brief, main changes revolves around the 24-month explorative outcomes: after analyses of 6- and 12-month outcomes we realized that results across work outcomes were heterogenous to a higher extent than expected. E.g., while the SAU group tended to have fastest RTW at 6-month follow-up, from explorative proportion over time-curves we realized that they might also tend to have a higher degree of recurrent sick-leave. Despite this, the SAU and INT groups still showed approx. the same number of weeks in work (when stability is disregarded) at 12-month follow-up. Followingly we speculate that the SAU group experiences faster RTW, but more recurrent sick leave. Therefore, we suggest that number of weeks in stable work is a better outcome, since this number is only high if RTW happens early, and if it is stable, and not disrupted by sick leave recurrence. We do though not know what stability threshold we should apply, and to *explore* this, we defined, prior to 24-month analyses, three different outcomes, with three different thresholds, see section 6.4. We plan these as sensitivity analyses.

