3.5 TIMING OF FINAL ANALYSIS

The researchers who will perform the 6- and 12-month outcome analyses (AH and JF) will be blinded from intervention group allocation, until the primary outcome and all 12-month follow-up outcome main analyses are completed. The true randomization group allocation is concealed, with values X, Y and Z reflecting group allocation in the blinded dataset. The randomization allocation variable conversion formula is until unblinding only known and hidden by an administrative co-worker, who will not perform or assist any analysis.

At the time of publication of SAP version 1, baseline distributional analyses, and unadjusted estimated marginal means-analyses of self-reported numerical secondary outcomes at 6-month follow-up (and only these) have been calculated *blinded*, but will not be published, since this was not complying with the SDAs, nor any SAP version.

All 24-month follow-up analyses will be conducted unblinded.

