6.8.2.7 REPORTING AND STATISTICAL METHODS TO HANDLE MISSING DATA

Same as 6.8.1.7.

6.8.3 ALL SELF-REPORTED, NUMERICAL OUTCOMES, AT 6-, 12-, AND 24-MONTH FOLLOW-UP AT (SECONDARY OUTCOMES ##4-7 AND PREDEFINED EXPLORATORY OUTCOMES ##16-48)

6.8.3.1 CALCULATION OF THE OUTCOME: SPECIFIC MEASUREMENT AND UNITS (AND TRANSFORMATION, WHERE APPLICABLE)

All outcomes are calculated as the sum of scores on the respective measurement scales.

All 6-month follow-up outcome analyses are calculating using baseline and 6-month follow-up observations.

All 12-month follow-up outcome analyses are calculating using baseline and 6- and 12-month follow-up observations.

All 24-month follow-up outcome analyses are calculating using baseline and 6-, 12-, and 24-month follow-up observations.

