6.8.3.2 SPECIFIC ANALYSIS METHOD AND RESULT PRESENTATION

Linear mixed-effects model with unstructured covariance. Results will be presented in pairwise group differences between outcomes, from the estimated marginal means from the model, and the confidence intervals of these differences.

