6.8.3.3 COVARIATE ADJUSTMENT

Only for stratification variables, see 6.1 “Covariate adjustment in general”.

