6.8.3.4 STATISTICAL METHOD ASSUMPTION CONTROL

Assumption: normal distribution of scores. Control: Visual inspection by plotting the score residuals.

Assumption: normal distribution of individuals’ score differences between baseline and follow-up. Control: Visual inspection by plotting the score difference residuals.

Assumption: Equality and homogeneity of variance. Control: Breusch Pagan test and Bartlett’s test are used to identify violations of these assumptions.

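### Questionnaire outcomes: the SAP bars the baseline score as a covariate and leaves the mixed model's baseline handling and contrast open, and two of its three readings lose precision

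*SAP*

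**What the plan says.** Section 6.1 sets the general rule: "Analyses will be adjusted for the three stratification variables, and no other, complying with RCT analysis guidelines". Section 6.8.3.3 applies it to all questionnaire outcomes without exception: "Only for stratification variables, see 6.1".

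Section 6.8.3.1 brings the baseline score in as one of the observations, for example "All 24-month follow-up outcome analyses are calculating using baseline and 6-, 12-, and 24-month follow-up observations".

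Section 6.8.3.2 gives the model as "Linear mixed-effects model with unstructured covariance" and the result as follows: "Results will be presented in pairwise group differences between outcomes, from the estimated marginal means from the model". It lists no fixed effects, does not say whether the arms share a baseline mean, and does not say whether the contrast is a level or a change. The assumption checks in 6.8.3.4 include the distribution of "score differences between baseline and follow-up".

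On timing, section 1.2 places this version "after analyses of 6- and 12-month outcomes we realized that results across work outcomes were heterogenous", and section 3.5 adds "All 24-month follow-up analyses will be conducted unblinded".

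**The concern.** A scale's own baseline score is usually among the strongest predictors of its follow-up score, and it has already been collected. The covariate rule shuts it out of the one place where its use would be explicit, and the model description does not secure its use in another way. Three readings fit the text:

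1. **Follow-up difference, separate baseline mean per arm.** On complete data the marginal-mean difference is simply the difference in follow-up means. Baseline then helps only through the handling of missing scores.
2. **Change contrast.** The check on score differences in 6.8.3.4 hints at this. Baseline is used, but less efficiently than by adjustment.
3. **Common baseline mean across arms.** Large-sample precision equals that of baseline adjustment, and 6.1 is respected.

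Two things are at stake. Readings 1 and 2 give wider intervals than the data allow, in comparisons already made at 0.0167. The readings can also give different estimates from the same data, so the main questionnaire result is not fixed, and the 24-month analysts will be unblinded.

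**Working it through.** **The plan's own figure.** Section 3.3 gives 198 per group (153 at power 0.8), for time to return to work only. It reproduces with the Schoenfeld formula under exponential times, medians of 210 and 315 days, and 730 days' accrual plus 365 days' follow-up:

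- Power 0.9: events = 4(2.394 + 1.282)²/(ln 1.5)² ≈ 329. With a mean event probability of (0.887 + 0.777)/2 = 0.832, this gives 197.5 per group.
- Power 0.8: 255 events, or 153.1 per group.

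The SAP gives no correlation, SD or target difference for any questionnaire, so those below are assumptions.

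**Inputs.** From the SAP: two-sided alpha 0.05/3 = 0.0167, so z = 2.394, and n = 198 or 153 per arm. Assumed: equal SD at both visits, a difference of 0.3 SD, correlation r = 0.4/0.5/0.6 given the stratification variables, and no attrition.

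**Formula.** SE = SD × √(2v/n), with v depending on the reading:

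- follow-up contrast, separate baseline means: v = 1
- change contrast: v = 2(1 − r)
- common baseline mean, or baseline as covariate: v = 1 − r²

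The follow-up contrast exceeds the adjusted variance by r². The change contrast exceeds it by 2(1 − r) − (1 − r²) = (1 − r)². Both excesses are positive for every r strictly between 0 and 1, so the assumed r affects only the size of the loss.

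| | r = 0.4 | r = 0.5 | r = 0.6 |
|---|---|---|---|
| v, follow-up | 1.00 | 1.00 | 1.00 |
| v, change | 1.20 | 1.00 | 0.80 |
| v, adjusted | 0.84 | 0.75 | 0.64 |
| Variance cut against follow-up, r² | 16% | 25% | 36% |
| Variance cut against change, (1 − r)/2 | 30% | 25% | 20% |
| Power, n = 198, follow-up | 72% | 72% | 72% |
| Power, n = 198, change | 63% | 72% | 83% |
| Power, n = 198, adjusted | 81% | 85% | 91% |
| Power, n = 153, follow-up | 59% | 59% | 59% |
| Power, n = 153, adjusted | 68% | 74% | 81% |

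Worked example, n = 198: for the follow-up contrast 0.3/√(2/198) = 2.985, and Φ(2.985 − 2.394) = 72%. Adjusted at r = 0.5, 0.3/√(1.5/198) = 3.447, and Φ(3.447 − 2.394) = 85%.

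**Simulation.** A two-occasion unstructured model was fitted by maximum likelihood on complete data (SD 10, 2,000 replicates per r). With separate baseline means, the follow-up marginal-mean difference matched the raw difference to within 4e-15. The variance ratio of the common-baseline model was 0.827/0.751/0.622 to the follow-up contrast and 0.704/0.775/0.780 to the change contrast, close to the formulas. Mean estimates were within 0.03 of the true zero. Stratification covariates and missing data were not simulated.

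**Missing follow-up.** Information-matrix calculations at r = 0.3/0.5/0.7 give the variance of each contrast relative to the common-baseline model:

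| | No missing | 30% missing (assumed) |
|---|---|---|
| Follow-up contrast | 1.10/1.33/1.96 | 1.07/1.23/1.67 |
| Change contrast | 1.54/1.33/1.18 | 1.38/1.23/1.12 |

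At r = 0.5 the variance cut is then 1 − 1/1.23 = 19% instead of 25%.

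**The case against.** The strongest reply is that baseline is not discarded. It is a response in an unstructured mixed model, which is an accepted longitudinal analysis, and with a common baseline mean it loses nothing and does not breach 6.1. That is right, and one sentence in 6.8.3.2 stating the constraint would be enough. But the constraint is not stated, and without it the follow-up contrast gains nothing from baseline on complete or imputed data.

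The change reading is weakly supported. Section 6.4 numbers each outcome as a scale at a visit, section 6.6 defines benefit by a higher or lower score, and only an assumption check points to change. The text leans towards a follow-up level. This stands, but it leaves the reading whose variance exceeds the adjusted one by r².

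The size is hypothetical, and the power figures ignore attrition although 6.8.3.7 plans 100 imputations. This also stands. Over two years r could be below 0.4; at r = 0.3 with 30% missing, the gain over the follow-up contrast is only about 7%.

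The plan's other provisions do not close the gap. Section 6.2 adjusts for a baseline score only if it is imbalanced at p ≤ 0.05 among the variables in 5.2, and that result cannot replace the main one. Both 5.2 and the imputation list in 6.8.3.7 name only the depression, anxiety, WSAS and PSS scores, so the other eight 24-month scales' own baselines appear in neither.

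Finally, changing the model after the 6- and 12-month analyses, with unblinded analysts, is itself a cost. That is true and calls for a dated, disclosed change. Leaving several models admissible for unblinded analysts is no safer.

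**Conclusion.** The concern holds. The covariate bar is explicit, the baseline handling and contrast are not fixed, and two of the three readings are less precise than the collected data allow at any r strictly between 0 and 1. At r = 0.4 to 0.6 with equal SDs and complete data, the avoidable variance is 16 to 36% under the follow-up reading and 30 to 20% under the change reading. Missing data shrink this without removing it.

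The consequence is limited. All readings are unbiased under randomisation, and the primary outcome and its sample size are unaffected. Taking section 1.2 to cover the questionnaires, only the twelve exploratory 24-month outcomes (#18, 20, 22, 24, 26, 29, 32, 35, 38, 41, 44 and 48) can still be fixed prospectively. The change should be made, but the validity of the trial does not depend on it. What the guideline cited in 6.1 says about baseline scores cannot be checked from the SAP and plays no part here.

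**What to change.** - In 6.1 and 6.8.3.3, permit the same scale's baseline value as a covariate where one was collected.
- In 6.8.3.2, list the fixed effects and choose one model: a common baseline mean with arm-by-visit terms at follow-ups only, or baseline as a covariate with the follow-ups as responses. State that the reported contrast is the between-arm difference at the visit that defines the outcome.
- Make this the main analysis for the twelve 24-month questionnaire outcomes, fixed and dated before those data are analysed.
- For the 6- and 12-month outcomes already analysed, including secondary outcomes #4 to #7, disclose the model and contrast used and report baseline-adjusted results as labelled supplementary analyses.

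The cost is a few sentences and no new data. The 24-month model may differ from the one used at 6 and 12 months, so the report should say so and give the date and reason, because the 24-month analyses are unblinded.

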6.2 SENSITIVITY ANALYSES IN GENERAL

As sensitivity analyses, all outcome analyses will be performed adjusted for any unbalanced baseline covariates, as defined in 5.2, *Baseline patient characteristics*.

Results of sensitivity analyses are only interpreted as supplements to the main analysis and will not substitute main results.

6.2.1 SENSITIVITY ANALYSES FOR QUESTIONNAIRE BASED, SELF-REPORTED DATA OUTCOME

As sensitivity analyses, self-reported data outcomes (questionnaire-based) will be calculated with all missing outcome data replaced with a value equalling the mean of the outcome variable ± 2 standard deviations, and participants who withdraw themselves from the study will be included in these analyses with all their data handled as missing.

6.2.2 SENSITIVITY ANALYSES FOR REGISTER DATA BASED OUTCOMES

For register data-based outcomes, sensitivity analyses will be performed including the participants who withdraw themselves from the study, included in these analyses with all their outcomes handled as either the worst possible (never returning to work) vs best possible (returning to work as soon as possible).

Furthermore, all outcomes of number of weeks in stable return to work (outcome number 9, 10, 11 and 12), are sensitivity analyses, exploring the robustness of number of weeks in work (stability disregarded), which is outcome number 13, pre-planned before study commencement.

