3.3 SAMPLE SIZE

Replicated from protocol follows:

³ <https://www.psykiatri-regionh.dk/Kvalitet-og-udvikling/udvikling/ibbis/Sider/IBBIS-forskning.aspx>

The sample size is based on a sample size calculation, using the 'Power and Sample Size' calculation programme⁴.

Type I error (α) risk

In each of the two RCTs we wish to conduct multiple comparisons (between 3 groups), and hence significance level must be as follows, due to Bonferroni correction:

$$\alpha = \frac{0,05}{3} = \frac{1}{60} = 0,0167$$

Type II error (β) risk

The organizational constellation of the interventions has not yet been trialled, and thus the desired power shall be set to:

$$\beta = 0,9$$

If it turns out that we cannot include enough participants, the power could be set to: $\beta = 0,8$

Hazard ratio (R)

The mean difference in time for return to work will be calculated as a hazard ratio. We estimate that as sufficient HR is

$$R = 1,5$$

since just 50 % faster return to work time in the intervention groups will convey a relevant economic benefit, due to the hence smaller loss of productivity.

Mean time to return to work (M_1)

Number of days from baseline to return to work is conservatively estimated to be 210 days, after an observed range from 104 to 210 days, in the control groups in three Dutch RCTs⁵⁻⁷, which were comparable to the control groups in the IBBIS RCTs.

Hence,

$$M_1 = 210$$

Inclusion time period (A)

We will include participants through 24 months,

$$A = 730[\text{days}]$$

Ratio between groups (m)

Ratio is 1:1:1, and hence $m = 1$

Follow-up time (F)

We will follow participants up for 365 days, in which they will contribute with risk time in the survival analysis, hence $F = 365$

Result

In each group, due to the above-mentioned variables, we need

198 participants per group, and with three groups that yields a need for, with power = 0.9,

⁴ <http://ps-power-and-sample-size-calculation.software.informer.com>

$$N = 198 \frac{\text{participants}}{\text{group}} \times 3 \frac{\text{groups}}{\text{trial}} = 594 \text{ participants}$$

If, in case of insufficient inclusion possibilities, power could be lowered to 0.8. In such case we would need the following number:

$$N = 153 \frac{\text{participants}}{\text{group}} \times 3 \frac{\text{groups}}{\text{trial}} = 459 \text{ participants}$$

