4 STATISTICAL PRINCIPLES

4.1 CONFIDENCE INTERVALS AND P-VALUES

For all outcomes, the three randomization groups are pairwise compared. Due to these multiple comparisons, we will calculate 98,3% confidence intervals, according to Bonferroni correction of desired α -level of 0,05 in testing of 3 hypotheses:

$$\alpha\text{-level: } 0,05 \times \frac{1}{3} \cong 0,0167 \Rightarrow \text{Confidence Interval: } 1 - 0,0167 \cong 98,33\%$$

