5 TRIAL POPULATION

5.1 WITHDRAWAL AND FOLLOW-UP

Due to legislative circumstances participants can withdraw consent, and followingly all person sensitive data on these subjects will be deleted, yet participant ID number (not CPR number, but generated for this research project) and randomization result will be stored. In sensitivity analyses these ID numbers will be included, as described in “handling of missing data”.

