6.7.1 HANDLING OF MISSING DATA IN REGISTERS

For RTW-outcomes (outcomes based on the DREAM register) we expected *no missing data*, due to the nature of the Dream Register, prior to study inception. Missing data should only be in case of a participant moving out of Denmark. We considered these events to be so rare in our data that we would handle such missing data as *missing completely at random*. Thus, no imputation or other correction was considered necessary. We will report proportion of data missing.

We will report number of censored participants per treatment group.

At the of this updated version 2a of the SAP, we have realized that some data were missing due to DREAM database errors, against expectation. We included the cases with missing data in sensitivity analyses to explore the potential impact of the missingness.

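### Sections 6.2.1 and 6.2.2 do not say which arm receives which missing-data extreme; read literally, all arms get the same one, which hardly tests a pairwise contrast when missingness is similar

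*SAP*

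**What the plan says.** Section 6.2.2 brings withdrawn participants back into the register outcomes with "all their outcomes handled as either the worst possible (never returning to work) vs best possible (returning to work as soon as possible". Section 6.2.1 analyses questionnaire outcomes with "all missing outcome data replaced with a value equalling the mean of the outcome variable ± 2 standard deviations", and counts withdrawn participants as missing throughout. Neither section mentions randomization group.

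Five other places bear on this:

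- **Target of inference (4.1):** "For all outcomes, the three randomization groups are pairwise compared", and "we will calculate 98,3% confidence intervals, according to Bonferroni correction".
- **What survives withdrawal (5.1):** personal data are deleted, but the ID number is kept and the "randomization result will be stored".
- **Main handling of missing data:** register outcomes are treated as missing completely at random without imputation (6.7.1, 6.8.1.7). Questionnaires are treated as missing at random, with 100 imputations (6.7.2, 6.8.3.7). The listed imputation variables do not include randomization group.
- **DREAM database errors (6.7.1):** "We included the cases with missing data in sensitivity analyses to explore the potential impact of the missingness". The values given to these cases are not stated.
- **Weight (6.2):** "Results of sensitivity analyses are only interpreted as supplements to the main analysis and will not substitute main results".

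**The concern.** Every result in this trial is a contrast between two arms. Giving the same extreme value to the missing participants of both arms moves both arm summaries together, and most of the movement cancels. The case that would hurt a conclusion is poor outcomes among the missing in one arm and good outcomes in the other. No analysis in the SAP specifies it: the main analyses assume missingness completely at random or at random, and the sensitivity runs, read literally, treat all arms alike.

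If opposite extremes were intended, the text is still too loose. With three arms and three pairs it does not say which arm gets which value. Section 3.5 makes all 24-month analyses unblinded, so that choice could be made after seeing group results. Either way, a reader could take two sensitivity results close to the main one as evidence of robustness that they do not give.

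**Working it through.** **Inputs.** From section 3.3: "198 participants per group, and with three groups that yields a need for, with power = 0.9"; hazard ratio 1.5; 210 days to return to work in controls (used as a median); accrual 730 days; follow-up 365 days. From 4.1: alpha 0.05/3 = 0.0167. Assumed, because the SAP gives no figures: withdrawal of 3 to 10% per arm for register outcomes; 20 to 40% missing for questionnaires.

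**1. The plan's own group size.** Two-sided Schoenfeld events at power 0.9: 4 × (2.394 + 1.282)² / (ln 1.5)² = 329. With medians of 210 and 315 days, uniform accrual and exponential times, the event probabilities are 0.887 and 0.777 (mean 0.832). Then 329 / (2 × 0.832) = 197.7, against 198 stated. At power 0.8, 255 events give 153.3, against 153 stated. This confirms the group size used below and nothing more.

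**2. A proportion, to show the mechanism.** Take 0.56 against 0.44 in work (illustrative), with 10% missing in each arm.

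- All worst: 0.9 × 0.56 − 0.9 × 0.44 = 0.108.
- All best: 0.108 + 0.10 − 0.10 = 0.108.
- Opposite extremes: 0.108 ± 0.10 = 0.008 to 0.208.

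With 5% missing in the intervention arm and 10% in control:

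- All worst: 0.95 × 0.56 − 0.9 × 0.44 = 0.136.
- All best: 0.136 + 0.05 − 0.10 = 0.086.
- Opposite extremes: 0.136 − 0.10 = 0.036 to 0.136 + 0.05 = 0.186.

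So same-direction runs do react to unequal missingness, but stay inside the opposite-direction range.

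**3. The primary outcome.** Simulated Cox hazard ratios, 198 per arm, control median 210 days, 365 days of follow-up, equal withdrawal in both arms. The 3% row and the last row come from 60 replicates, the others from 300.

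| True HR | Withdrawn per arm | All worst / all best | Opposite extremes |
|---|---|---|---|
| 1.5 | 3% | 1.51 / 1.51 | 1.37 to 1.67 |
| 1.5 | 10 (5%) | 1.46 / 1.46 | 1.24 to 1.72 |
| 1.5 | 20 (10%) | 1.42 / 1.42 | 1.03 to 1.97 |
| 1.0 | 10 (5%) | 1.00 / 1.00 | 0.85 to 1.17 |
| 1.0 | 10% | 1.02 / 1.02 | 0.75 to 1.40 |

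A run with 150 replicates gave 1.25 to 1.72 at 5% and 1.05 to 1.97 at 10%.

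**4. What this does to significance.** By 365 days the control event probability is 1 − 2^(−365/210) = 0.70. Two such arms give 2 × 198 × 0.70 = 277 events, and SE(log HR) = √(4/277) = 0.12. Significance at 0.0167 needs HR ≥ exp(2.394 × 0.12) = 1.33.

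- Same-direction, 1.46: z = 0.378/0.12 = 3.2, significant.
- Adverse opposite case, 1.24: z = 0.215/0.12 = 1.8, not significant.

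In the 150-replicate run at 5%, the share of significant trials was 80% and 81% in the same-direction runs and 34% in the adverse opposite run. The Monte Carlo SE is √(0.34 × 0.66/150) = 0.04, so read 34% as roughly 26 to 42%.

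**5. Questionnaires.** Take an observed difference of −0.30 SD, 30% missing per arm and one replacement value for both arms.

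- Same sign in both arms: 0.7 × (−0.30) = −0.21 SD for either sign.
- Opposite signs: a shift of 0.3 × 2 + 0.3 × 2 = 1.2 SD, giving −1.41 or +0.99 SD.
- Precision in the same-sign run: the SD grows by √(0.7 + 4 × 0.3 × 0.7) = 1.24, so z is (0.7/1.24) × √(1/0.7) = 0.67 of its complete-case value.

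With 20% missing in the intervention arm and 40% in control, the same-sign runs give −0.61 and +0.19, against −1.41 and +0.99 for opposite signs.

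**The case against.** The strongest reply is that the SAP never says all arms move together. Its wording names two extremes and is silent on arm, so opposite assignment is not excluded. That stands: the defect is an unspecified allocation, and same-direction runs are the plain reading rather than a stated rule.

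Further points that stand:

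- The SAP does not present these analyses as bounds. They explore impact and cannot replace the main result. Missingness will be reported by group (6.7), so a reader can see an imbalance.
- Same-direction runs are informative when missingness differs. At 3% withdrawal in the intervention arm and 8% in control, all worst gives 1.65 and all best 1.40.
- Section 6.2.1 does not say whether the mean is overall or by arm. With arm means and equal missingness, the same-sign difference stays at −0.30 SD instead of shrinking. The 1.2 SD shift is unaffected, but it describes a single-time mean difference, not the planned mixed model.
- For register outcomes the SAP expected almost no missing data, and at 3% per arm the opposite range is only 1.37 to 1.67.

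What does not stand is the idea that silence is harmless. If opposite extremes were meant, the pairs and directions still have to be written down.

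**Conclusion.** The point holds as a gap in specification that leaves a sensitivity analysis weak. Read literally, the planned runs say little about arm-specific missingness when arms lose similar proportions, and nothing else in the SAP covers it. For the primary outcome, 5% withdrawal per arm in the adverse opposite case is enough to take a true hazard ratio of 1.5 below significance. For questionnaires the possible shift is far larger than the illustrative effect.

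Two stronger inferences are tempting and are not supported. One is that the SAP fixes the same direction for all arms and offers the result as a bound; it does neither. The other is that the primary conclusion could reverse. At 5% the average opposite-direction estimates stay on the same side of 1 when the true ratio is 1.5 (1.24), and within the non-significant range when it is 1.0 (0.85 to 1.17). At 10% the opposite range reaches about 1.03 in the first case and roughly the significance limits (0.75 to 1.40) in the second, so the margin depends on withdrawal rates that the SAP does not give. A change of sign is readily reached only for questionnaires, and only under extreme assumptions.

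This should be changed, but it concerns supplementary analyses and not the primary estimate.

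**What to change.** **Section 6.2.2:** keep the two existing runs. For each pairwise comparison add arm A worst with arm B best, and the reverse. That is 3 pairs × 2 = 6 further runs per outcome. Storage of the allocation of withdrawn participants makes this possible.

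**Section 6.2.1:** add the same crossed scenarios (mean + 2 SD in one arm, mean − 2 SD in the other, and the reverse), stating whether the mean is overall or by arm. Alternatively, add arm-specific shifts from −2 SD to +2 SD to the imputed values within the 100 planned imputations, with randomization group in the imputation model, and report the shift at which the conclusion changes. Both signs are needed: shifts of 0 to 2 SD only would reach 0.3 × 2 = 0.6 SD at 30% missing, half the crossed case. Also say how withdrawn participants enter, since only their ID and allocation survive.

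**Timing:** section 1.2 shows that 6- and 12-month outcomes were analysed before this version, so any rerun for those outcomes must be labelled post hoc.

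**Cost:** somewhat more analysis, and wide, less reassuring ranges in a supplementary table. No new data are needed and the main results are untouched.
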